## **5 SAMPLE SIZE AND POWER**

The incidence rate of treatment related select high grade AE is 0.5-3% of nivolumab 3mg/kg every two weeks with infusion time no less than 30 minutes based on the Checkmate 153 study

which published in ASCO 2016, and a PPK model predicted overall nivolumab exposures across participants with a wide range of body weight (35-160 kg) for a 240 mg every 2 weeks flat dose to be similar to that from 3 mg/kg every 2 weeks, so we assume that the incidence rate of treatment related select high grade AE is similar in both 3 mg/kg every 2 weeks and 240mg every 2 weeks.

In order to further characterize the frequency and outcome of the rather infrequent treatment related select adverse of high grade (Grade 3-5), the current study will treat approximately 400 participants (assuming 340 non-HBV infected participants and 60 HBV infected participants) with nivolumab. The 95% confidence intervals of the incidence rate of high grade (grade 3-5) treatment related select adverse events were listed as below table. With the screen failure rate of 15%, totally 470 participants will be screened.

Table 5.1 shows the CI using Clopper Pearson methods for a sample size of 340 non-HBV infected participants and all treated participants.

**Table 5.1: 95% Confidence Intervals of Adverse Event Rate**

AE Incidence Rate	Non-HBV (340 participants)	Overall (400 participants)
0.5%	0.07%, 2.11%	0.06%, 1.79%
1%	0.32%, 2.98%	0.27%, 2.54%
3%	1.63%, 5.71%	1.56%, 5.18%

## **6 STUDY PERIODS, TREATMENT REGIMENS AND POPULATIONS FOR ANALYSES**

### **6.1 Study Periods**

See Core Safety SAP.

### **6.2 Treatment Regimens**

All subjects will be treated with nivolumab.

Table 6.1 shows selection and timing of dose.

**Table 6.1: Selection and Timing of Dose**

Study Treatment	Unit dose strength(s)/Dosage level(s)	Dosage formulation Frequency of Administration	Route of Administration
Nivolumab	240 mg	Q2 weeks	IV

### **6.3 Populations for Analyses**

The following defined population will apply to pooled tumor types and individual tumor histology and molecular genotype, unless otherwise specified:

- **Enrolled Participants:** All participants who signed an informed consent form and were registered into the IRT.
- **Treated Participants:** All enrolled participants who received at least one dose of study drug.
- **Response Evaluable Participants:** All treated participants who have baseline and at least one on-study evaluable tumor measurement.
- **Non-HBV infected participants:** All treated participants with HBVsAg negative by serum testing.
- **HBV infected participants:** All treated participants with HBVsAg positive by serum testing.
- **Biomarker participants:** All treated participants with available tissue [REDACTED] samples.

## **7 STATISTICAL ANALYSES**

Statistical analyses will be performed for all treated participants by HBV status and pooled unless otherwise specified.

Demographic and baseline laboratory results will be summarized using descriptive statistics for all treated participants. Baseline characteristics, including demographics (age, gender, geographic location, race/ethnicity) and clinical characteristics (date of diagnosis, disease stage, liver function status, performance status, co-morbidity/prognostic indicators, location of metastases) will be collected at the time of treatment initiation for each cohort. General descriptive statistics, including mean and standard deviation (SD) for continuous variables, count and percentage for categorical variables will be used extensively to examine these variables.

### **7.1 General Methods**

Unless otherwise noted, the following subsections describe tabulations of discrete variables, by the frequency and proportion of subjects falling into each category by HBV status and pooled. Percentages given in these tables will be rounded and, therefore, may not always sum to 100%. Percentages less than 0.1 will be indicated as ‘<0.1’. Continuous variables will be summarized by HBV status and pooled using the mean, standard deviation, median, minimum and maximum values.

Time to event distribution will be estimated using Kaplan Meier techniques. This will be done for overall survival, time to treatment failure, progression-free survival and duration of response. Median survival time along with 95% CI will be constructed based on a log-log transformed CI for the survivor function  $S(t)$ . Rates at fixed time points will be derived from the Kaplan Meier estimate and corresponding confidence interval will be derived based on Greenwood formula for variance derivation and on log-log transformation applied on the survivor function  $S(t)$ .

Since CA209870 is a single arm study, analyses by HBV status will consist of three groups (“Non-HBV”, “HBV” and “Total”) unless otherwise specified. [REDACTED]

The conventions to be used for imputing partial dates for analyses requiring dates are described in [Section 8](#).

## 7.2 Study Conduct

Unless otherwise specified, the study conduct data will be presented on all treated participants by HBV status and pooled.

### 7.2.1 Relevant Protocol Deviations

The relevant protocol deviations will be summarized, by HBV status and pooled. The following programmable deviations from inclusion and exclusion criteria will be considered as relevant protocol deviations. Non-programmable relevant eligibility and on-treatment protocol deviations, as well as significant (both programmable and non-programmable) eligibility and on-treatment protocol deviations will be reported through [REDACTED].

At Entrance:

- Participants without histologically- or cytologically-documented NSCLC (SQ or NSQ) who present with Stage IIIB/Stage IV disease.
- Participants without recurrent or progressive disease following multimodal therapy (radiation therapy, surgical resection, or definitive chemo-radiotherapy for locally advanced disease).
- Participants who didn't receive at least 1 to 2 prior systemic therapies.
- Participants with baseline ECOG PS>1.
- Participants with HBV DNA $\geq$ 500 IU/ml if HBsAg $^+$ .
- Participants without measurable disease at baseline by CT or MRI RECIST 1.1 criteria (radiographic tumor assessment performed within 28 days of first dose of study drug) or clinically apparent disease that the investigator can follow for response per RECIST 1.1.

On-study:

- Participants receiving prohibited and/or restricted treatments.

A by-subject listing will be provided.

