### **6.1 Inclusion Criteria**

- 1) Signed Written Informed Consent
  - a) Participants must have signed and dated an IRB/IEC-approved written informed consent form in accordance with regulatory and local guidelines. This must be obtained before the performance of any protocol-related procedures that are not part of normal participant care.
  - b) Participants must be willing and able to comply with scheduled visits, treatment schedule, laboratory tests, and other requirements of the study.
- 2) Type of Participant and Target Disease Characteristics
  - a) Participants with histologically- or cytologically-documented NSCLC (SQ or NSQ) who present with Stage IIIB/Stage IV disease (according to version 8 of the International Association for the Study of Lung Cancer Staging Manual in Thoracic Oncology), or with recurrent or progressive disease following multimodal therapy (radiation therapy, surgical resection, or definitive chemo-radiotherapy for locally advanced disease).
    - i) Participants must have experienced disease progression or recurrence after one systemic therapies for advanced or metastatic disease.
    - ii) Each subsequent line of therapy must be preceded by disease progression. A switch of an agent within a regimen in order to manage toxicity does not define the start of a new line of therapy.
    - iii) Maintenance therapy following platinum doublet-based chemotherapy is not considered as a separate regimen of therapy.
  - iv) Participants who received platinum-containing adjuvant, neoadjuvant or definitive chemoradiation therapy given for locally advanced disease, and developed recurrent (local or metastatic) disease within 6 months of completing therapy are eligible.
  - v) Participants with recurrent disease > 6 months after completing a platinum-containing adjuvant, neoadjuvant or definitive chemoradiation therapy given for locally advanced disease, who also subsequently progressed during or after a systemic regimen given to treat the recurrence, are eligible.
    - (1).EGFR testing is not required if ALK or KRAS test is positive.
    - (2).ALK testing is not required if EGFR or KRAS test is positive.

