### **7.3.2 *Demographics and Baseline Characteristics***

Descriptive statistics of the following baseline characteristics will be summarized by HBV status and pooled for all treated participants.

- Age
- Gender
- Race
- Baseline Eastern Cooperative Oncology Group (ECOG) performance status
- Tobacco Use
  - Type of Tobacco
  - Tobacco Use Status
  - Number Per Day
  - Number of Years
- Electronic Cigarette Use

- Initial Disease Diagnosis
  - Time from initial diagnosis to study treatment first dose
  - Disease Stage at Initial Diagnosis
  - Cell type
  - Histological Grade
- Current Disease Diagnosis
  - Time from diagnosis to study treatment first dose
  - Disease Stage at Study Entry: Stage IIIB/IV/Recurrent
  - Subtype of Disease
- Target Lesions at screening
  - Lesion Type
  - Organ Code
  - Procedure Code
  - Measurement
- Non-Target Lesions at Screening
  - Lesion Type
  - Organ Code
  - Procedure Code
- Pulse Oximetry
- Laboratory Test Results HIV
- Laboratory Test Results HBV DNA
- Laboratory Test Results HCV and HBV

A by subject listing will be provided separately for all the above mentioned variables.

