### **7.3.5 *Prior Therapy***

Descriptive statistics of prior therapies will be summarized by HBV status and pooled for all treated participants.

- Prior Surgery Related to Cancer
  - Subjects with surgery (yes/no)
  - Type of Surgery
  - Time from last surgery to study treatment first dose
- Prior Radiotherapy
  - Subjects with radiotherapy (yes/no)
  - Site of Radiotherapy
  - Time from last therapy stop to study treatment first dose
- Prior Systemic Cancer Therapy
  - Subjects with systemic cancer therapy (yes/no)
  - Number of regimens for each subject
  - Setting of regimen (adjuvant therapy/metastatic disease/neo-adjuvant therapy)
  - Line of Therapy (First Line/second line/third line/not applicable/unknown)
  - Best response to regimen (CR/PR/SD/PD/unable to determine/not applicable) - The last response will be considered as best response to regimen in case of multiple records per subject.
  - Time from last therapy stop to study treatment first dose

A by-subject listing will be provided separately for prior surgery related to cancer, prior radiotherapy and prior systemic cancer therapy.

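### SAP 7.2.1 splits the either/or disease criterion of Protocol 6.1 2(a) into two separate deviations, so participants eligible by one route alone are listed as deviators

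*SAP*

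**What the plan says.** Protocol 6.1, inclusion 2(a), is a single criterion. After requiring documented NSCLC presenting at Stage IIIB or IV, it continues "or with recurrent or progressive disease following multimodal therapy". Either route is enough.

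SAP 7.2.1 introduces a list of programmable departures from the eligibility criteria, each to be treated as a relevant deviation. The opening entry is "Participants without histologically- or cytologically-documented NSCLC (SQ or NSQ) who present with Stage IIIB/Stage IV disease". The next stands as a deviation in its own right and negates the other route: "Participants without recurrent or progressive disease following multimodal therapy (radiation therapy, surgical resection, or definitive chemo-radiotherapy for locally advanced disease" (closing bracket omitted).

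No word links them. The third entry covers those who did not "receive at least 1 to 2 prior systemic therapies". The section promises a summary for each HBV group and overall, plus a by-subject listing. It also names a separate route, with its destination redacted, for non-programmable relevant deviations and for significant deviations of both kinds.

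Elsewhere the SAP treats the disease routes as alternatives. SAP 7.3.2 has the baseline item "Disease Stage at Study Entry: Stage IIIB/IV/Recurrent".

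On prior therapy, footnote A to the schematic (Protocol Figure 5.1-1, SAP Figure 2.1) restricts participants without an EGFR or ALK alteration to one systemic therapy. For those with an alteration it calls for two, including a TKI and chemotherapy.

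**The concern.** Negating an either/or criterion gives one condition: neither route is met. The SAP instead negates each half and lists both. A participant with Stage IV disease at diagnosis, who progressed on one systemic regimen and never had surgery, radiotherapy or chemoradiation, fits the second-line population the protocol describes. That participant still meets the second deviation entry.

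At stake is the credibility of one table and one listing. SAP 9 puts the planned analyses in the Clinical Study Report unless otherwise noted. The protocol stresses full adherence to eligibility (end of Section 6.2) and allows no waivers (Section 9). A deviation table that mixes eligible participants with real deviators overstates non-adherence and hides the cases that matter.

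**Working it through.** The plan states no figure on this point, so the check is logical.

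**Disease criterion.** Let A = documented NSCLC at Stage IIIB/IV, and B = documented NSCLC with recurrence or progression after multimodal treatment (the two halves of Protocol 6.1 2(a)).

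- Protocol: eligible if A or B, so a deviation is (not A) and (not B).
- SAP 7.2.1, each entry standing alone: entry 1 = not A; entry 2 = not B; listed if (not A) or (not B).

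| Pattern | Protocol deviation? | Entry 1 | Entry 2 | Result |
|---|---|---|---|---|
| A and B | no | no | no | correct |
| A only | no | no | yes | wrongly listed |
| B only | no | yes | no | wrongly listed |
| neither | yes | yes | yes | correct |

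The two rules disagree when exactly one route is met. On the literal reading, 2 of the 3 eligible patterns are wrongly listed.

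Entry 1 has another reading: it may target only Stage IIIB/IV participants whose NSCLC lacks histological or cytological documentation. The B-only pattern is then not listed, and 1 of the 3 eligible patterns (A only) is still wrongly listed by entry 2. These are counts of logical patterns, not of people.

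With one merged flag, (not A) and (not B), only the last row is listed.

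**Prior-therapy entry.** The wording allows at least four readings: none received; fewer than two; outside one to two; or a minimum that depends on molecular type. Against footnote A:

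| Group, therapies counted | Footnote A | None | Fewer than 2 | Outside 1–2 | Minimum by type |
|---|---|---|---|---|---|
| No EGFR/ALK, 0 | deviation | listed | listed | listed | listed |
| No EGFR/ALK, 1 | eligible | – | wrongly listed | – | – |
| No EGFR/ALK, 2 | deviation | missed | missed | missed | missed |
| EGFR/ALK, 0 | deviation | listed | listed | listed | listed |
| EGFR/ALK, 1 | deviation | missed | listed | missed | listed |
| EGFR/ALK, 2 (TKI and chemotherapy) | eligible | – | – | – | – |

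No reading reproduces footnote A.

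The entry also does not say which regimens count. SAP 7.3.5 records "Setting of regimen (adjuvant therapy/metastatic disease/neo-adjuvant therapy" (closing bracket omitted), so more than one count is possible. Inclusion 2(a)(iv) covers those who had platinum-containing adjuvant, neoadjuvant or chemoradiation treatment "and developed recurrent (local or metastatic) disease within 6 months of completing therapy are eligible". Such a participant has one therapy if every setting counts, but none if only regimens for metastatic disease count, and would then be listed on all four readings. Inclusion 2(a)(v) covers later recurrences in those "who also subsequently progressed during or after a systemic regimen given to treat the recurrence, are eligible". They have two therapies or one, depending on the same choice.

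**The case against.** The strongest defence is the lead-in to the SAP 7.2.1 list, which speaks of departures from the eligibility criteria. A participant who satisfies 2(a) by either route has not departed from it. The two entries sit side by side and follow the two halves of that criterion in order, and SAP 7.3.2 shows that the authors knew the routes were alternatives. A programmer might well join them, and the table mock-ups are in the Data Presentation Plan, which is not available here.

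This makes the intention plausible but does not repair the text. The lead-in says that each listed item counts as a deviation; it does not say that two of them must occur together. The measurable-disease entry in the same list keeps both of its alternatives inside one entry, so the list does carry an either/or when that is meant.

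Four stronger inferences are tempting, and the documents do not support them:

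- **That results are affected.** The populations in SAP 6.3 rest on dosing, HBV serology, tumor measurements and samples. None drops deviators, and the study tests no formal hypothesis.
- **That a large share of participants would be listed.** No document gives the proportion who meet only one route, so any number would be invented.
- **That participants with too many prior therapies would go unseen.** The programmable list need not cover every criterion. Some of these cases may be reported through the non-programmable and significant-deviation route. SAP 7.3.5 already tabulates the number of regimens, their setting and the line of therapy, with a by-subject listing.
- **That inclusions 2(b) and 2(b)(i) contradict each other.** The first concerns sensitizing EGFR mutations or ALK rearrangement and the second non-sensitizing EGFR mutations, so a difference in wording between them is not in itself a conflict.

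**Conclusion.** The second entry of SAP 7.2.1 is wrong as written on any reading of the first. It lists every eligible Stage IIIB/IV participant without prior multimodal treatment. On the literal reading, the first entry adds those who qualify only by recurrence or progression. The number of participants cannot be derived from the documents. The consequence is limited to one descriptive summary and its listing. It should be corrected before programming, but it does not threaten the safety or efficacy results.

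The conclusion assumes that each entry is programmed as it stands. If the Data Presentation Plan already joins the two, the SAP text still needs to say so.

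The prior-therapy entry is a secondary wording defect: it is ambiguous and matches footnote A on none of the readings tried.

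**What to change.** 1. Replace the first two entries with one flag: participants who have neither documented NSCLC at Stage IIIB/IV nor documented NSCLC that recurred or progressed after multimodal treatment. The cost is one line of SAP text and one derived flag. Stage at entry and prior surgery, radiotherapy and systemic therapy are already summarized under SAP 7.3.2 and 7.3.5.

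2. Reword the prior-therapy entry by molecular type, reconciled with footnote A and with inclusions 2(a)(iv)–(v) and 2(b), including the provision for indeterminate or unavailable genotype. State which regimens count. This review does not choose the eligibility rule. Where counting lines needs judgement (maintenance, switches for toxicity, experimental regimens, the 6-month rule), leave the case to the non-programmable route already named in SAP 7.2.1. This takes more work than the first change because it has branches and depends on agreed wording.

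Neither change needs new data collection.

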## 7.3 Study Population

Unless otherwise specified, the study population data will be presented on all treated participants by HBV status and pooled.

A pre-treatment and end of treatment disposition tables will be summarized using all enrolled participants and all treated participants respectively. The efficacy endpoints such as overall

survival (OS), Best Overall Response (BOR), Objective Response Rate (ORR), Time to Treatment Failure (TTF) and Progression-Free Survival (PFS) will be summarized using all treated participants by HBV status and pooled. The duration of Response (DOR) and duration of SD will be summarized based on all response evaluable participants.

Safety analysis will be based on all treated participants by HBV status and pooled. All the biomarker data will be analyzed based on all biomarker participants by HBV status and pooled.

### **7.3.1 *Subject Disposition***

The total number of subjects enrolled (treated or not) will be presented along with the reason for not being treated. This summary will be presented on all enrolled participants pooled together.

Number of subjects who discontinued treatment along with corresponding reason will also be tabulated.

In addition, the below summary will be provided.

- **Pre-Treatment Status:** The total number of subjects entered into the treatment phase and not entering the treatment phase will be presented along with the primary reason for all enrolled participants.
- **Subject Status - End of Treatment:** Subject continuing in the treatment period of this study and primary reason for not continuing in the treatment period will be presented for all treated participants.

Also, total number of subjects by country and investigational site will be provided.

A by subject listing of pre-treatment, end of study and end of treatment status will be provided separately.

### **7.3.2 *Demographics and Baseline Characteristics***

Descriptive statistics of the following baseline characteristics will be summarized by HBV status and pooled for all treated participants.

- Age
- Gender
- Race
- Baseline Eastern Cooperative Oncology Group (ECOG) performance status
- Tobacco Use
  - Type of Tobacco
  - Tobacco Use Status
  - Number Per Day
  - Number of Years
- Electronic Cigarette Use

- Initial Disease Diagnosis
  - Time from initial diagnosis to study treatment first dose
  - Disease Stage at Initial Diagnosis
  - Cell type
  - Histological Grade
- Current Disease Diagnosis
  - Time from diagnosis to study treatment first dose
  - Disease Stage at Study Entry: Stage IIIB/IV/Recurrent
  - Subtype of Disease
- Target Lesions at screening
  - Lesion Type
  - Organ Code
  - Procedure Code
  - Measurement
- Non-Target Lesions at Screening
  - Lesion Type
  - Organ Code
  - Procedure Code
- Pulse Oximetry
- Laboratory Test Results HIV
- Laboratory Test Results HBV DNA
- Laboratory Test Results HCV and HBV

A by subject listing will be provided separately for all the above mentioned variables.

### **7.3.3 Physical Measurements**

Descriptive statistics of the following physical measurements will be summarized by HBV status and pooled for all treated participants for each time-point.

- Height (cm)
- Weight (kg)
- BMI (kg/m^2)
- ECOG Performance Status

A by-subject listing will be provided.

### **7.3.4 Medical History**

General medical history and disease specific history will be listed by subject.

### **7.3.5 *Prior Therapy***

Descriptive statistics of prior therapies will be summarized by HBV status and pooled for all treated participants.

- Prior Surgery Related to Cancer
  - Subjects with surgery (yes/no)
  - Type of Surgery
  - Time from last surgery to study treatment first dose
- Prior Radiotherapy
  - Subjects with radiotherapy (yes/no)
  - Site of Radiotherapy
  - Time from last therapy stop to study treatment first dose
- Prior Systemic Cancer Therapy
  - Subjects with systemic cancer therapy (yes/no)
  - Number of regimens for each subject
  - Setting of regimen (adjuvant therapy/metastatic disease/neo-adjuvant therapy)
  - Line of Therapy (First Line/second line/third line/not applicable/unknown)
  - Best response to regimen (CR/PR/SD/PD/unable to determine/not applicable) - The last response will be considered as best response to regimen in case of multiple records per subject.
  - Time from last therapy stop to study treatment first dose

A by-subject listing will be provided separately for prior surgery related to cancer, prior radiotherapy and prior systemic cancer therapy.

